7.3.4. Electronic Serious Adverse Event (eSAE) Reporting Process

- Site personnel record all SAE data on the applicable eCRFs and from there transmit the SAE information to Gilead PVE within 24 hours of the investigator's knowledge of the event. Detailed instructions can be found in the eCRF completion guidelines.
- If it is not possible to record and submit the SAE information electronically, because the eCRF database cannot be accessed or is not available (including at study-start), record the SAE on the paper SAE reporting form and submit within 24 hours to:

Gilead PVE

Email: PPD

or

Fax: PPD

- As soon as it is possible to do so, any SAE reported via paper must be transcribed on the applicable eCRFs according to instructions and within the timelines outlined in the eCRF completion guidelines.
- If an SAE has been reported via a paper form because the eCRF database has been locked, no further action is necessary.
- For fatal or life-threatening events, copies of hospital case reports, autopsy reports, and other documents are also to be submitted by email or fax when requested and applicable. Transmission of such documents should occur without personal subject identification, maintaining the traceability of a document to the subject identifiers.
- Additional information may be requested to ensure the timely completion of accurate safety reports.
- Any medications necessary for treatment of the SAE must be recorded onto the concomitant medication section of the subject's eCRF and the SAE narrative section of the Safety Report Form eCRF.

7.4. Gilead Reporting Requirements

Depending on relevant local legislation or regulations, including the applicable US FDA Code of Federal Regulations, the European Union (EU) Clinical Trials Directive (2001/20/EC) and relevant updates, and other country-specific legislation or regulations, Gilead may be required to expedite to worldwide regulatory agencies reports of SAEs, serious adverse drug reactions (SADRs), or suspected unexpected serious adverse reactions (SUSARs). In accordance with the EU Clinical Trials Directive (2001/20/EC), Gilead or a specified designee will notify worldwide regulatory agencies and the relevant IEC in concerned Member States of applicable SUSARs as outlined in current regulations.

Assessment of expectedness for SAEs will be determined by Gilead using reference safety information specified in the investigator's brochure or relevant local label as applicable.

All investigators will receive a safety letter notifying them of relevant SUSAR reports associated with any study drug. The investigator should notify the IRB or IEC of SUSAR reports as soon as is practical, where this is required by local regulatory agencies, and in accordance with the local institutional policy.

7.5. Clinical Laboratory Abnormalities and Other Abnormal Assessments as Adverse Events or Serious Adverse Events

Laboratory abnormalities without clinical significance are not recorded as AEs or SAEs. However, laboratory abnormalities (eg, clinical chemistry, hematology, and urinalysis) that require medical or surgical intervention or lead to study drug interruption, modification, or discontinuation must be recorded as an AE, as well as an SAE, if applicable. In addition, laboratory or other abnormal assessments (eg, electrocardiogram, x-rays, vital signs) that are associated with signs and/or symptoms must be recorded as an AE or SAE if they meet the definition of an AE or SAE as described in Sections 7.1.1 and 7.1.2. If the laboratory abnormality is part of a syndrome, record the syndrome or diagnosis (eg, anemia), not the laboratory result (ie, decreased hemoglobin).

Laboratory abnormalities that do not require medical intervention or action are generally not considered AEs.

Severity should be recorded and graded according to the DAIDS Table for Grading the Severity of Adult and Pediatric Adverse Events, Version 2.1 dated July 2017. For AEs associated with laboratory abnormalities, the event should be graded on the basis of the clinical severity in the context of the underlying conditions; this may or may not be in agreement with the grading of the laboratory abnormality.

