3.3. Study Treatments

In Part A, approximately 600 participants who meet all eligibility criteria may be randomized in a 1:1:1 ratio into 1 of the following treatment groups:

Treatment Group 1: continued SOC therapy together with IV RDV 200 mg on Day 1 followed by IV RDV 100 mg on Days 2, 3, 4, and 5

Treatment Group 2: continued SOC therapy together with IV RDV 200 mg on Day 1 followed by IV RDV 100 mg on Days 2, 3, 4, 5, 6, 7, 8, 9, and 10

Treatment Group 3: continued SOC therapy

In Part B, an additional approximately 1000 participants who meet all of the eligibility criteria may receive:

Extension Treatment Group: continued standard of care therapy together with IV RDV 200 mg on Day 1 followed by IV RDV 100 mg on Days 2, 3, 4, 5, 6, 7, 8, 9, and 10 unless treatment Group 1 of Part A is selected. If treatment for 5 days is selected, all participants in the Extension Treatment Group and all new participants will be reassigned to receive treatment for a total of 5 days. National and local regulatory authorities will be informed.

Participants in Part A of the study will be the primary efficacy population. Participants enrolled in Part B, will have data reported descriptively at study completion.

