3.4. Duration of Treatment

Participants will receive study treatment with RDV for 5 days (treatment group 1), study treatment with RDV for 10 days (treatment group 2), no RDV (treatment group 3), or either 5 or 10 days (Extension Treatment Group). If the participant is discharged, RDV treatment will stop at that time.

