3.5. Discontinuation Criteria

Study drug dosing in an individual subject will be placed on hold and may be discontinued, following a review of all available clinical data by the medical monitor and discussion with the investigator, if any of the following occurs:

- Any SAE or \geq Grade 3 AE suspected to be related to RDV
- Any elevations in ALT $> 5 \times$ ULN; or ALT $> 3 \times$ ULN and total bilirubin $> 2 \times$ ULN, confirmed by immediate repeat testing
- Creatinine Clearance < 30 mL/min

Discontinuation of study medication is not a seriousness criterion.

Subjects who discontinue the study medication should be encouraged to remain in the study and attend study visits as described in Sections 6.3, 6.4, and 6.5.

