8.5.2. Secondary Analyses

The secondary endpoint of proportion of participants with treatment emergent AEs will be compared between each of the RDV groups and standard of care group in Part A using a Fisher's Exact test. The point estimates of the treatment differences and the associated 95% confidence intervals will be provided. Other endpoints of interest related to proportion of participants will be compared between treatment groups in Part A using a chi-square test or Fisher's Exact test. Efficacy endpoints that are measured as time to first event will be compared between treatment groups using a competing risk model (with death as the competing risk) and continuous endpoints will be compared between treatment groups using a Wilcoxon rank sum test or analysis of variance model.

The 7-point ordinal scale of clinical status and other efficacy endpoint of interest will be summarized descriptively for Part B.

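### A laboratory result that interrupts dosing is a mandatory AE on RDV, but the same result is largely left to judgment on SOC; this can raise the TEAE proportion on RDV, probably by little

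*Protocol*

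**What the plan says.** Protocol Section 7.5 has two stand-alone triggers that make a laboratory abnormality a mandatory AE. The first covers abnormalities "that require medical or surgical intervention". The second follows directly: "or lead to study drug interruption, modification, or discontinuation must be recorded as an AE". The section adds that abnormal assessments with signs or symptoms are AEs if they meet the AE definition. Its default for the rest is: "Laboratory abnormalities that do not require medical intervention or action are generally not considered AEs".

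Protocol Section 3.5 supplies the drug action: "Study drug dosing in an individual subject will be placed on hold and may be discontinued" when a listed criterion is met. The laboratory criteria are ALT above 5 × ULN, ALT above 3 × ULN with total bilirubin above 2 × ULN (with repeat confirmation), and "Creatinine Clearance < 30 mL/min".

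The control arm is described in Section 3.3 as "Treatment Group 3: continued SOC therapy", and Section 3.4 confirms that it receives no RDV. Section 5.1.2 says there is no blinding.

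The TEAE proportion is the only secondary endpoint (Section 8.1.3). Section 8.5.2 says it "will be compared between each of the RDV groups and standard of care group in Part A using a Fisher's Exact test". Section 8.6.2 counts any AE that starts in the window and does not set aside AEs recorded only because dosing was stopped.

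**The concern.** The drug-action trigger depends on treatment. An RDV participant on dosing who reaches a Section 3.5 laboratory threshold has dosing held, and the result must then be entered as an AE. A SOC participant with the same result has nothing to hold. Unless the result needs intervention, or is accompanied by signs or symptoms and meets the AE definition, the investigator decides, knowing the arm.

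An excess of TEAEs on RDV could then come partly from the recording rule. It would fall on hepatic and renal laboratory events, and Section 1.5 names transaminase elevation as the pertinent specific risk and describes kidney findings in animals. The rule acts only while dosing continues: to Day 5 in Group 1, to Day 10 in Group 2, and not after discharge. The two RDV groups are therefore exposed to it for different lengths of time. Aligning the TEAE window or the start of AE collection across arms would not remove the difference, because it lies in what counts as an AE.

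**Working it through.** **The plan's own figure.** The documents give no TEAE rate, hold rate or power for the secondary endpoint, so there is no figure on this point to reproduce. The sample size of 200 per group is from Protocol Section 8.9. Its stated power of more than 85% concerns the primary endpoint. It checks out at 88.8% with the printed formula, but nothing below rests on it.

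**The same result in each arm**

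| Laboratory result | RDV, during dosing | SOC |
|---|---|---|
| Needs intervention | Mandatory AE | Mandatory AE |
| Signs or symptoms, and meets AE definition | Mandatory AE | Mandatory AE |
| Meets a 3.5 threshold, none of the above | Mandatory AE through the hold | Investigator judgment |

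Only the last row differs. It changes the TEAE proportion only for a participant with no other TEAE.

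**Assumed inputs**

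- p0: risk of any other TEAE, equal in both arms; 30%, 45% or 60%.
- h: probability, equal in both arms, of a silent hold-threshold result. This means a result that would trigger a hold, needs no intervention and would not be recorded on SOC; 1%, 2%, 5% or 10%.
- The silent result is independent of other TEAEs, and there is no true difference between arms.

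**Formula**

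p_SOC = p0; p_RDV = p0 + (1 − p0)h; artefact = (1 − p0)h.

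At p0 = 45%:

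- h = 1%: 0.55 × 0.01 = 0.55 points, or 1.1 extra participants per 200
- h = 2%: 0.55 × 0.02 = 1.1 points, or 2.2 per 200
- h = 5%: 0.55 × 0.05 = 2.75 points, or 5.5 per 200
- h = 10%: 0.55 × 0.10 = 5.5 points, or 11 per 200

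**Exact rejection rate of the two-sided Fisher test at 0.05, 200 against 200 (artefact in points in brackets)**

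| h | p0 = 30% | p0 = 45% | p0 = 60% |
|---|---|---|---|
| 0 | 3.9% (0) | 3.9% (0) | 3.8% (0) |
| 1% | 4.1% (0.7) | 4.1% (0.55) | 3.9% (0.4) |
| 2% | 4.8% (1.4) | 4.4% (1.1) | 4.1% (0.8) |
| 5% | 9.7% (3.5) | 7.1% (2.75) | 5.5% (2.0) |
| 10% | 28.2% (7.0) | 17.1% (5.5) | 10.9% (4.0) |

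Up to h = 2% the rejection rate stays below the nominal 5% at all three base rates. At h = 5% it is above 5% at all three.

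**Scope of the trigger.** The post-baseline laboratory tests scheduled within dosing are Days 3 and 5 for Group 1, and Days 3, 5, 8 and 10 for Group 2 (Section 6.4). Section 6.6 allows others by clinical need or local practice. A result after the last dose interrupts nothing, so for the same patients h is no larger in Group 1 than in Group 2.

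**The case against.** The strongest reply is that the asymmetry is narrow and its consequence minor. Most of this stands.

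- A reader might infer that hold-level results on SOC are not counted. Section 7.5 does not say so. Results needing intervention, and symptomatic results that meet the AE definition, are AEs in every arm. The default for the rest is qualified by the word generally. Section 4.3 excludes ALT or AST above 5 × ULN and creatinine clearance below 50 mL/min at entry, so a SOC participant who reaches a hold threshold has usually worsened and may well be recorded.
- A reader might infer a seriously inflated false-positive rate. An artefact of 4 or 6 points at a 45% base rate needs silent results in 7.3% (4/0.55) or 10.9% (6/0.55) of participants, as a background rate in both arms. The documents give no support for that. Section 1.5 describes the RDV transaminase elevations seen so far as transient and no higher than Grade 2.
- A reader might infer a biased test of 5 against 10 days. Section 8.5.2 compares the TEAE proportion for each RDV group with SOC; no formal test between the RDV groups is stated for this endpoint. The difference in exposure to the rule affects only how the two estimates look side by side.
- Section 8.6.3 summarises treatment-emergent laboratory abnormalities by grade, with a definition that does not depend on drug action. The hepatic and renal laboratory signal can be read there. This is a real but partial safeguard, because that table is not the secondary endpoint.
- The bias runs against RDV, so it cannot create false reassurance about the drug.
- The supplied SAP covers Part B only. The Part A primary analysis SAP that it cites and the eCRF completion guidelines are not supplied, so an existing supportive analysis or entry instruction cannot be ruled out.

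What remains is that recording is mandatory in one arm and discretionary in the other for the same value, in an unblinded trial, and that it feeds the only secondary endpoint.

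**Conclusion.** The asymmetry follows directly from Sections 7.5, 3.5 and 3.4, and it can bias the TEAE proportion upward on RDV. Its direction is clear but its size is not known. At a 45% base rate and 200 per arm, the artefact is 0.55 to 1.1 points if silent hold-threshold results occur in 1% to 2% of participants, which barely moves the test. It is 2.75 points at 5% and 5.5 points at 10%, where it would matter. All of this rests on assumed rates, on equal true risk in the arms, and on independence from other TEAEs. If silent results cluster in participants who have other TEAEs anyway, the artefact is smaller; it can never exceed h. The effect is likely small unless such results are common. The point deserves a cheap correction and does not undermine the safety comparison.

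**What to change.** **If AE recording can still be changed.** Keep the existing drug-action trigger in Section 7.5. Add one sentence: any laboratory result that meets a Section 3.5 laboratory threshold is recorded as an AE in every arm, whatever action follows. Carry it into the eCRF completion guidelines.

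**If the data are already collected.** SAP Sections 2.1.2 and 2.1.3 describe the Part A analyses as done, so this is the practical route. Add one supportive TEAE comparison in which results meeting a Section 3.5 laboratory threshold, taken from the common laboratory dataset, count as events in all arms. Section 6.4 schedules these tests on the same days in every arm until discharge. State in advance whether repeat confirmation of ALT is required, and apply the same choice everywhere, because Section 3.5 ties the repeat test to the dosing decision.

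**What not to change.** Do not delete the drug-action trigger. Section 6.11.1 allows dosing to stop for toxicity in the investigator's judgment, and without the trigger a laboratory result below the 3.5 thresholds that stops RDV would no longer have to be recorded. That part of the asymmetry therefore remains and should be acknowledged. The hold rule itself is not in question.

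**Cost.** One sentence and a few more AE entries on SOC, or one extra table. If the Part A SAP already contains such an analysis, a cross-reference is enough.

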7.6. Special Situations Reports

7.6.1. Definitions of Special Situations

Special situation reports include all reports of medication error, abuse, misuse, overdose, occupational exposure, drug interactions, exposure via breastfeeding, unexpected benefit, transmission of infectious agents via the product, counterfeit of falsified medicine, and pregnancy regardless of an associated AE.

Medication error is any unintentional error in the prescribing, dispensing, preparation for administration or administration of an investigational product while the medication is in the control of a health care professional, patient, or consumer. Medication errors may be classified as a medication error without an AE, which includes situations of missed dose; medication error with an AE; intercepted medication error; or potential medication error.

Abuse is defined as persistent or sporadic intentional excessive use of an investigational product by a subject.

Misuse is defined as any intentional and inappropriate use of an investigational product that is not in accordance with the protocol instructions or the local prescribing information.

An overdose is defined as an accidental or intentional administration of a quantity of an investigational product given per administration or cumulatively which is above the maximum recommended dose as per protocol or in the product labeling (as it applies to the daily dose of the subject in question). In cases of a discrepancy in drug accountability, overdose will be established only when it is clear that the subject has taken the excess dose(s). Overdose cannot be established when the subject cannot account for the discrepancy except in cases in which the investigator has reason to suspect that the subject has taken the additional dose(s).

Occupational exposure is defined as exposure to an investigational product as a result of one's professional or non-professional occupation.

Drug interaction is defined as any drug/drug, drug/food, or drug/device interaction.

Unexpected benefit is defined as an unintended therapeutic effect where the results are judged to be desirable and beneficial.

Transmission of infectious agents is defined as any suspected transmission of an infected agent through a Gilead investigational product.

Counterfeit or falsified medicine: Any investigational product with a false representation of:
a) its identity, b) its source, or c) its history.

7.6.2. Instructions for Reporting Special Situations

7.6.2.1. Instructions for Reporting Pregnancies

The investigator should report pregnancies in female study subjects that are identified after initiation of study drug and throughout the study, including the post study drug follow-up period, to Gilead PVE using the pregnancy report form within 24 hours of becoming aware of the pregnancy.

Gilead PVE

Email: PPD

or

Fax: PPD

Refer to Section 7.3 and the eCRF completion guidelines for full instructions on the mechanism of pregnancy reporting.

The pregnancy itself is not considered an AE nor is an induced elective abortion to terminate a pregnancy without medical reasons.

Any premature termination of pregnancy (eg, a spontaneous abortion, an induced therapeutic abortion due to complications or other medical reasons) must be reported within 24 hours as an SAE. The underlying medical reason for this procedure should be recorded as the AE term.

A spontaneous abortion is always considered to be an SAE and will be reported as described in Sections 7.3.2. Furthermore, any SAE occurring as an adverse pregnancy outcome post study must be reported to Gilead PVE.

The subject should receive appropriate monitoring and care until the conclusion of the pregnancy. The outcome should be reported to Gilead PVE using the pregnancy outcome report form. If the end of the pregnancy occurs after the study has been completed, the outcome should be reported directly to Gilead PVE. Gilead PVE contact information is as follows: email:

PPD and fax: PPD

Pregnancies of female partners of male study subjects exposed to Gilead study drugs must also be reported and relevant information should be submitted to Gilead PVE using the pregnancy and pregnancy outcome forms within 24 hours. If the end of the pregnancy occurs after the study has been completed, the outcome should be reported directly to Gilead PVE, fax number

PPD or email PPD

Refer to [Appendix 3](#) for Pregnancy Precautions, Definition for Female of Childbearing Potential, and Contraceptive Requirements.

7.6.2.2. Reporting Other Special Situations

All other special situation reports must be reported on the special situations report form and forwarded to Gilead PVE within 24 hours of the investigator becoming aware of the situation. These reports must consist of situations that involve study drug and/or Gilead concomitant medications, but do not apply to non-Gilead concomitant medications.

Gilead PVE

Email: PPD

or

Fax: PPD

Special situations involving non-Gilead concomitant medications do not need to be reported on the special situations report form; however, special situations that result in AEs due to a non-Gilead concomitant medication, must be reported as an AE.

Any inappropriate use of concomitant medications prohibited by this protocol should not be reported as “misuse,” but may be more appropriately documented as a protocol deviation.

Refer to Section 7.3 and the eCRF completion guidelines for instructions on special situation reporting.

All clinical sequelae in relation to these special situation reports will be reported as AEs or SAEs at the same time using the AE eCRF and/or the SAE report form. Details of the symptoms and signs, clinical management, and outcome will be reported, when available.

8. STATISTICAL CONSIDERATIONS

8.1. Analysis Objectives and Endpoints

8.1.1. Analysis Objectives

The purpose of this study is to provide RDV to participants with moderate COVID-19.

The primary objective of this study is as follows:

- To evaluate the efficacy of 2 RDV regimens compared to standard of care (SOC), with respect to clinical status assessed by a 7-point ordinal scale on Day 11

The secondary objective of this study is as follows:

- To evaluate the safety and tolerability of RDV compared to SOC

8.1.2. Primary Endpoint

The primary endpoint of this study is:

- Clinical status assessed by a 7-point ordinal scale on Day 11

8.1.3. Secondary Endpoints

The secondary endpoint of this study is:

- The proportion of participants with treatment emergent adverse events

8.1.4. Other Endpoints of Interest

Other endpoints of interest are:

- The proportion of participants with negative SARS-CoV-2 PCR
- Time to clinical improvement (days): clinical improvement is defined as a ≥ 2 -point improvement in clinical status (7-point ordinal scale) from Day 1
- Time to ≥ 1 -point improvement (days) from baseline clinical status
- Time to recovery: defined as an improvement in clinical status from a baseline score of 2 through 5 to a score of 6 or 7, or an improvement from a baseline score of 6 to a score of 7
- Time to modified recovery: defined as an improvement in clinical status from a baseline score of 2 through 4 to a score of 5, 6, or 7, or an improvement from a baseline score of 5 to a score of 6 or 7, or an improvement from a baseline score of 6 to a score of 7

- Time to room air: defined as an improvement in clinical status from a baseline score of 2 through 4 to a score of 5, 6, or 7
- Duration of oxygen therapy (days)
- Shift in oxygen support status from baseline
- Duration of hospitalization (days)
- All-cause mortality at Day 28

- The proportion of participants in the Extension Treatment Group with treatment emergent adverse events

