4.2. Inclusion Criteria

Subjects must meet all of the following inclusion criteria to be eligible for participation in this study:

- 1) Willing and able to provide written informed consent (participants ≥ 18 years of age) or assent (participants ≥ 12 and < 18 years of age) prior to performing study procedures. For participants ≥ 12 and < 18 years of age, a parent or legal guardian willing and able to provide written informed consent prior to performing study procedures
- 2) Aged ≥ 18 years (at all sites), or aged ≥ 12 and < 18 years of age weighing ≥ 40 kg (where permitted according to local law and approved nationally and by the relevant institutional review board [IRB] or independent ethics committee [IEC])
- 3) SARS-CoV-2 infection confirmed by PCR ≤ 4 days before randomization
- 4) Currently hospitalized and requiring medical care for COVID-19
- 5) SpO₂ $> 94\%$ on room air at screening
- 6) Radiographic evidence of pulmonary infiltrates
- 7) Men and women of childbearing potential who engage in heterosexual intercourse must agree to use protocol specified method(s) of contraception as described in [Appendix 3](#).

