6.9. Ordinal Scale

The ordinal scale is an assessment of the clinical status at a given study day. Each day, the worst (ie, lowest ordinal) score from the previous day will be recorded, ie, on Day 3, the lowest ordinal score from Day 2 is obtained and recorded for Day 2. The scale is as follows:

- 1) Death

- 2) Hospitalized, on invasive mechanical ventilation or ECMO
- 3) Hospitalized, on non-invasive ventilation or high flow oxygen devices
- 4) Hospitalized, requiring low flow supplemental oxygen
- 5) Hospitalized, not requiring supplemental oxygen - requiring ongoing medical care (COVID-19 related or otherwise)
- 6) Hospitalized, not requiring supplemental oxygen - no longer requires ongoing medical care (other than per protocol RDV administration)
- 7) Not hospitalized

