6.2. Efficacy Endpoints of Interest

Efficacy endpoints of interest include endpoints based on clinical status assessed by a 7-point ordinal scale. The endpoint will be derived by combining the available death, hospital discharge alive and ordinal scale assessment reported by the site, where death supersedes discharge alive and discharge alive supersedes the ordinal scale score reported by the site. The proportion of participants for each ordinal scale category is expressed as percentages for presentation purpose.

Sites were instructed to report the worst ordinal scale category for each day. Therefore, the ordinal scale result on the day the participant was discharged alive does not necessarily reflect Not hospitalized (7). The definition of clinical status based on the 7-point ordinal scale is defined as follows:

- If a participant dies while hospitalized (as recorded on the Death eCRF and Hospitalization eCRF), the endpoint on the day of death and all subsequent days through Day 28 will be set to Death (1)
- If the participant is discharged alive, the endpoint on the day of discharge alive and all subsequent days through Day 28 will be set to Not hospitalized (7)
- If the participant is discharged alive and dies on the same day or a later day (as recorded on the Death eCRF and Hospitalization eCRF), the endpoint on the day of discharge alive and all subsequent days until the day of death will be set to Not hospitalized (7). On the day of death and all subsequent days through Day 28, the endpoint will be set to Death (1),

Every effort will be made to obtain clinical status data for all participants prior to discharge alive. The last known clinical status will be used for days with missing clinical status (eg, where the reason for Hospital Discharge is not "Discharged Alive" and the participant has not died). All post-baseline days with missing ordinal scale score, from Day 2 to Day 14 and Day 28, will use the previous last known clinical status.

Efficacy endpoints of interest include

- Clinical status on Days 1 to 14, Day 28 and last available assessment
- Change in clinical status on Days 5, 7, 11, 14, 28, and last available assessment
- Time to clinical improvement (days): Clinical improvement is defined as a ≥ 2-point improvement from baseline clinical status or discharged alive on the 7-point ordinal scale using the definition specified above.

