- Percentage of participants with a ≥ 2-point improvement or discharged alive based on the 7-point ordinal scale using the definition specified above on Day 5, Day 7, Day 11, Day 14, Day 28, and last available assessment
- Time to \geq 1-point improvement (days) from baseline clinical status on the 7-point ordinal scale using the definition specified above.
- Percentage of participants with a ≥ 1-point improvement based on the 7-point ordinal scale using the definition specified above on Day 5, Day 7, Day 11, Day 14, Day 28 and last available assessment
- Time to recovery based on the 7-point ordinal scale using the definition above, where recovery is defined as an improvement from a baseline score of 2 through 5 to a score of 6 or 7, or an improvement from a baseline score of 6 to a score of 7
- Percentage of participants with recovery based on the 7-point ordinal scale using the definition specified above on Day 5, Day 7, Day 11, Day 14, Day 28 and last available assessment
- Number of days of oxygen support while hospitalized through discharge alive, death or Day 14 based on the 7-point ordinal scale reported values (See Appendix 2). This summary will present results separately for participants who died on or prior to Day 14 and those who were discharged alive on or prior to Day 14 and will include:

Days on invasive mechanical ventilation

Days on high-flow oxygen devices

Days requiring low-flow supplemental oxygen

Because oxygen support status was collected only while the participant was in the hospital, if a participant was discharged alive and died afterwards, the participant will be included only in the summary for participants discharged alive. Oxygen support status is defined based on the 7-point ordinal scale (See Appendix 2)

- Shift in oxygen support status from baseline to Days 5, 7, 11, 14, 28 and last available assessment
- Duration of hospitalization (days) (duration from hospital admission and duration from Day 1). Duration of hospitalization is calculated through Days 11 and 28 for participants who were discharged alive prior to Days 11 and 28, respectively. If participants were rehospitalized for COVID-19 related reasons, the hospitalization discharge information is entered in the eCRF database using the latest hospitalization admission.
- All-cause mortality

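### The protocol's 2-point definition of clinical improvement cannot be met from baseline score 6; the Part B SAP repairs this without declaring a change, and the rule used in Part A is not shown

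*Protocol*

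**What the plan says.** Protocol 3.1 and 8.1.4 list time to clinical improvement among the other endpoints of interest. The event is a gain of at least 2 points, "improvement in clinical status (7-point ordinal scale) from Day 1", with no alternative route. The top category in Protocol 6.9 is "7) Not hospitalized". Score 6 is a hospitalized participant who is off oxygen and needs no further medical care apart from study dosing.

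In the same endpoint list, recovery and modified recovery each end with a clause for that starting point: "or an improvement from a baseline score of 6 to a score of 7". The 2-point endpoint has no such clause.

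Protocol 8.5.2 sets the between-group method: "Efficacy endpoints that are measured as time to first event will be compared between treatment groups using a competing risk model". Deaths are handled there as the competing event.

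The SAP supplied covers Part B only (SAP 1). Its section 6.2 defines the event as a gain of at least 2 points, written as "improvement from baseline clinical status or discharged alive on the 7-point ordinal scale using the definition specified above". The matching percentage endpoint is worded the same way: "improvement or discharged alive based on the 7-point ordinal scale using the definition specified above on Day 5". SAP 6.3 reports no changes from the efficacy analysis in the protocol. SAP 2.1.2 says that the Part A primary analysis followed a separate SAP dated 25 May 2020, which is not among the documents.

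**The concern.** Live discharge is the best outcome on this scale. Under the protocol wording, someone who starts at 6 and goes home on Day 2 is scored as not improved through Day 28. The drafters foresaw this starting score, since two neighbouring definitions make room for it.

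Two rules therefore stand under one endpoint name, and the SAP does not say so. For Part B this is a documentation gap. For Part A it leaves open which rule lies behind a randomized comparison. If the protocol wording was used, each arm contains some participants who cannot have the event, and its reported incidence of improvement is too low.

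**Working it through.** **The plan's own figure.** The only stated power figure is for the primary endpoint (Protocol 8.9): more than 85% for an odds ratio of 1.8 with 200 v 200 at two-sided 0.05. With the assumed SOC distribution shifted by proportional odds and averaged over the two arms, 1 − Σp³ = 0.8752. Then z_β = √(400 × (ln 1.8)² × 0.8752 / 12) − 1.96 = 1.21, a power of 88.8%. The figure reproduces and does not depend on this point.

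**Is the event reachable?** Maximum gain = 7 − baseline score.

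| Baseline | Maximum gain | Protocol rule (≥ 2) | Part B SAP rule (≥ 2 or discharged alive) |
|---|---|---|---|
| 2 | 5 | reachable | reachable |
| 3 | 4 | reachable | reachable |
| 4 | 3 | reachable | reachable |
| 5 | 2 | reachable | reachable |
| 6 | 1 | impossible | reachable |

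From scores 2 to 5, discharge already gives a gain of at least 2. The SAP's added phrase therefore changes the time to clinical improvement only for baseline 6.

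**Ceiling.** If a share q starts at 6, the proportion who can ever have the event under the protocol wording is 1 − q: 99%, 98%, 95% and 90% for q = 1%, 2%, 5% and 10%. The documents give no value for q, so these are assumptions.

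**Illustrative size.** Assumptions: discharge stands in for improvement, discharge hazards are constant, death is ignored, and baseline-6 participants are discharged at the same rate as the others. Inputs from Protocol 8.9: 40% of SOC not hospitalized at Day 11, and odds ratio 1.8.

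- RDV at Day 11: odds 1.8 × 0.4/0.6 = 1.2, so 1.2/2.2 = 54.5%.
- Hazards: SOC −ln(0.6)/11 = 0.0464; RDV −ln(0.4545)/11 = 0.0717.
- Day 28 incidence when every discharge counts, 1 − exp(−28h): SOC 72.8%, RDV 86.6%, difference 13.8 points.
- Protocol wording, non-events kept at risk to Day 28: multiply each by (1 − q).

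| q | SOC | RDV | Difference |
|---|---|---|---|
| 0% | 72.8% | 86.6% | 13.8 |
| 2% | 71.3% | 84.8% | 13.5 |
| 5% | 69.1% | 82.2% | 13.1 |
| 10% | 65.5% | 77.9% | 12.4 |

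**Dependence on censoring.** The protocol states no censoring rule for this endpoint. SAP 6.2.1 censors participants without the event at the last non-missing ordinal assessment. If that removes baseline-6 participants from the risk set at discharge, the event hazard becomes (1 − q)h. At q = 10% the estimates are 1 − exp(−28 × 0.9 × 0.0464) = 69.0% for SOC and 1 − exp(−28 × 0.9 × 0.0717) = 83.6% for RDV. Both are still too low, but the difference is 14.6 points and has not shrunk. An estimate made this way is also not held to the 1 − q ceiling, which applies to the true proportion with the event.

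**The case against.** Several points on the other side stand.

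- The only SAP supplied already counts discharge alive. A reader might infer that discharges from score 6 were in fact scored as never improving. The documents do not support that: it is untrue of Part B, and the Part A SAP is not available and may have carried the same repair. For the same reason they do not establish that the Part A and Part B figures are non-comparable.
- Entry requires a participant to be "Currently hospitalized and requiring medical care for COVID-19", which nearly excludes score 6. Baseline 6 should be uncommon. It is not ruled out: screening may precede randomization by up to 2 days (Protocol 6.2.1), and the ordinal scale is first scheduled on Day 1 (Appendix 2).
- Because randomization is unstratified, a reader might infer that an imbalance in baseline-6 share creates a spurious treatment effect. It does not. Chance imbalance is sampling error. At q = 5% its SD is √(2 × 0.05 × 0.95/200) = 2.2 points, and this is already contained in the standard error of the difference, √(0.691 × 0.309/200 + 0.822 × 0.178/200) = 4.2 points.
- A reader might also infer that the treatment difference must shrink. That depends on the unstated censoring rule.
- The stakes are low. The endpoint is neither primary nor secondary, no multiplicity-adjusted claim rests on it, and the 1-point, recovery and modified-recovery endpoints all credit a move from 6 to 7. Part B is descriptive.
- Part A had been analysed when this SAP was written (SAP 2.1.2, 2.1.3). Redefining its endpoint now would be a change made after the results were known.

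None of this makes the event reachable from score 6 under the protocol wording, or explains why SAP 6.3 is silent.

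**Conclusion.** The point holds in a limited form. As worded in Protocol 3.1 and 8.1.4, clinical improvement is impossible from baseline 6; this follows from the scale alone. The Part B SAP corrects it but does not list the correction as a change. The rule applied in Part A cannot be determined from these documents.

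If Part A used the protocol wording, incidence is understated in both arms by an amount that depends on q. With non-events kept at risk, the loss in the RDV–SOC difference is about 0.3 points at q = 2% and 0.7 points at q = 5%, and zero if nobody started at 6. These sizes rest on an assumed q and on the simple hazard model above. Primary and secondary results are unaffected.

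**What to change.** 1. In Protocol 3.1 and 8.1.4, add *or discharged alive* to the definition of clinical improvement, matching SAP 6.2.
2. In SAP 6.3, declare that the definition differs from the protocol and say why. If the SAP is already final, record this in the clinical study report, as SAP 1 provides.
3. State which rule the Part A analyses used, and report the number of participants at baseline score 6 by arm.
4. If Part A used the protocol wording, keep that result and add the corrected definition as a labelled sensitivity analysis, with the censoring rule stated. It should not replace the analysis already performed.

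The cost is a phrase in two protocol sections, a sentence in the SAP, one count, and at most one re-derived endpoint. Discharge is already recorded, so no new data are needed. If no one was at baseline 6, the results do not change and only the wording needs correcting.
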